**Figure 7 Different Scenarios for Self-controlled Risk Interval Design**

[figure not shown]

IRR, incidence rate ratio.

## 9.6 Data Management

The following transformation steps (T) will be implemented (Figure 8):

**Figure 8. Data Transformation Process**

CDMs, common data models;  $D_n$ , data type; ETL, extract, transform, and load; FAIR, findable, accessible, interoperable, and reusable; SAP, statistical analysis plan,  $T_n$ , transformational step (for explanation, see below).

### 9.6.1 T1: Syntactic Harmonisation (ETL)

T1: Syntactic harmonisation through an extract, transform, and load (ETL) process of native data into the ConcePTION CDM ([ConcePTION Study 2020](#)). In this CDM, data are represented using a common structure, but the content of the data remain in their original format. The CDM version that will be used was [v2.2](#), which is available as an open-source CDM. The CDM was developed as part of the IMI-ConcePTION project (project number IMI-821520). The ETL process has various structured steps as described in [Thurin et al \(2021\)](#):

- 1 Data access partners (DAPs) will be asked to share the data dictionaries of their data banks (tables and variable names/structure) with the principal investigator of the study.
- 2 Based on the data dictionaries of the data banks, an interview will be conducted by the Principal Investigator to explore what action(s) prompt the creation of a record, what is missing, and the context of each of the data banks.
- 3 Metadata (descriptive data about the data sources and databanks), data dictionaries, and interview answer sheets will be uploaded in the VAC4EU FAIR (findable, accessible, interoperable, and reusable) data catalogue, according to the metadata structure for electronic health data that was defined in IMI-ConcePTION and the EMA-funded MINERVA project.
- 4 An overview will be created of all the required study variables and definitions in order to create the code lists to identify the outcomes and covariates (see T2).

- 5 Instructions for the ETL design will be provided by the scientific coordinator, these instructions will comprise the required CDM tables, mandatory variables, the calendar period over which data need to be extracted, and the code lists for the data to be extracted.

Once the ETL design will be approved, it will be executed by each DAP using its programming language. The output files will be CSV (comma-separated values) files. Once the ETL is conducted, Level 1 and 2 data quality checks will be conducted to measure the integrity of the ETL, as well as internal consistency within the context of the CDM.

- 1 Level 1 data checks will be performed to assess the completeness and content for each variable in all CDM tables to ensure that the mandatory variables contain data and conform to the formats specified by the CDM specifications.
- 2 Level 2 data checks will be performed to assess the logical relationship and integrity of data values within a variable, or between 2 or more variables within and between tables.

### **9.6.2 T2: Semantic Harmonisation**

To reconcile differences between terminologies and native data availability, a shared semantic foundation will be applied for the creation of study variables. This is a multistep process:

- 1 Definition of study variables, which will be done using an event definition form and will be a living document that will be closed upon AZD1222 PASS ending.
- 2 Initial code lists will be created using the VAC4EU CodeMapper tool (<https://vac4eu.org/codemapper/>) which was developed during the IMI-ADVANCE project to assist in the creation of code sets from event definitions for several coding systems simultaneously while keeping a record of the complete mapping process.
- 3 Study variables will be named in a standard hierarchical fashion based on body system.
- 4 Review of the codes by DAPs.
- 5 5. Consolidation: Comments from DAPs will be consolidated by the study team.
- 6 Based on the relevant diagnostic medical codes and keywords, the algorithms will be constructed to operationalise the measurement of each study variable. These algorithms could differ by database, as the components relevant for the study variables may differ.
- 7 During the T2 step, transformations will occur for a series of steps related to completion of missing features in the data, eg, dose of vaccines, sorting on record level, combination of concepts for algorithm, and rule-based creation of study variables on a personal level for the study population (specific, if needed, per DAP).
- 8 Once the study variables are created, Level 3 checks will be deployed, which will be targeted to assess the patterns of study variables.

### 9.6.3 T3: Application of the Epidemiological Study Design

Based on the creation of the study variables on a person level or a medicines level, epidemiological designs will be applied. Specifically, matching on specific variables and selection based on inclusion and exclusion criteria.

### 9.6.4 T4: Statistical Analysis

This step in the data transformation pipeline produced statistical estimates such as descriptives (counts, percentages), distributions (mean, percentiles), and rates (prevalence, incidence). This was conducted using R.

#### 9.6.4.1 Scripting and Deployment

The analytical R scripts that produced the T2-T4 steps will be produced on VAC4EU GitHub for version control; links to the latest script will be distributed to DAPs for local deployment. Any issues will be notified, and the data engineers who are responsible for the R code will work with the local DAP to resolve issues. Scripts will be developed independently, based on data engineering programmes and the codebook in R (by University Medical Center Utrecht [UMCU]) will be validated using SAS (by RTI Health Solutions), comparing the output from both analysis programs was against each other for consistency.

### 9.6.5 T5: Results and Pooling After Processing

The aggregated results that will be produced through T4 will be uploaded to the Digital Research Environment (DRE) for pooled analyses and visualisation (T5, [Figure 8](#)). The DRE will be made available through VAC4EU and UMCU ([The anDREa consortium 2021](#)). The DRE is a Microsoft Azure cloud-based, research environment with double authentication where researchers can collaborate using data that are stored and organised securely. VAC4EU can use this facility through the UMCU tenant. UMCU is responsible for data processing and data security.

## 9.7 Data Analysis

In accordance with the recommendations of the American Statistical Association, the International Committee for Medical Journal Editors ([ICMJE 2019](#)), and expert opinion on the misuse of significance testing ([Greenland et al 2016](#), [Nature editorial 2019](#), [Rothman and Lash 2021](#)), we avoid relying on statistical significance to interpret study results. Instead of a dichotomous interpretation based on p-values and significance testing, we rely on a quantitative interpretation that considers the magnitude, precision, and possible bias in the estimates that we derive and report. We believe that this is a more appropriate approach than one that ascribes to chance any result that does not meet conventional criteria for statistical significance.

Detailed methodology for summary and statistical analyses of data collected in this study will be documented in a SAP, which will be finalised before any comparative analyses begin. The

SAP may modify the plans outlined in the protocol; any major modifications of primary endpoint definitions or their analyses would be reflected in a protocol amendment.

Analyses will be conducted separately within each contributing database, and pooling will occur using meta-analytic methods, if appropriate, at the end of the study (Section 9.7.11). Data extraction and analysis of AESIs are planned to occur periodically during the study period.

### **9.7.1 Descriptive Analysis of Subjects Who Received AZD1222**

The analyses described below will address primary objective 1.

Baseline characteristics (eg, demographics, medical history, comedications) of subjects in the *matched population* (ie, subjects vaccinated with AZD1222 and the 3 different comparator cohorts) will be described for the overall study population and for the specific populations of interest.

To describe potential differences in the baseline characteristics of AZD1222 vaccinees across the study period, descriptions will also be stratified by sequential 3-month periods since the start of the study.

In order to understand the impact of censoring follow-up for individuals rather than for the matched pairs, the follow-up time by matching covariates for AZD1222 and each comparator cohort will be described.

For continuous variables, means, standard deviations, medians, and other quartiles will be estimated. For categorical variables, counts and proportions will be estimated. The missingness of variables will also be described.

### **9.7.2 Descriptive Analysis of Second COVID-19 Vaccine Use**

The analyses described below will address primary objective 2.

- Among subjects who received dose 1 of AZD1222 (ie, *all AZD1222 vaccinated first dose population*) and those who received dose 1 of an mRNA vaccine (ie, *all mRNA vaccinated first dose population*), descriptive measures will be used to characterise patterns of second COVID-19 vaccine use over the study period. These distributions will be described overall and in sequential 3-month periods since the start of the study period.
- Description of the patterns of second COVID-19 vaccine will include the following:
  - Counts and proportions of subjects who received only the first dose of AZD1222
  - Counts and proportions of subjects who received a second dose of COVID-19 vaccine, specifying whether it was the AZD1222 vaccine or another COVID-19 vaccine and type (brand name)

- Among those who received 2 doses: the time (days) between the first and second doses will be described as a continuous variable (mean, standard deviation, median, quartiles, min, and max), as well as categorically (< 2, 2-4, 5-8, 9-12, 13-18, > 18 weeks)
- Patterns of second COVID-19 vaccine use will be described for the general study population and subgroups of special interest.

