## 7. RATIONALE AND BACKGROUND

The novel coronavirus SARS-CoV-2 (severe acute respiratory syndrome coronavirus 2), the cause of coronavirus disease 2019 (COVID-19), has led to a global pandemic. AZD1222 (called Vaxzevria® in Europe) is a vaccine that was developed to prevent COVID-19.

Coronaviruses are enveloped viruses with positive-sense single-stranded RNA genomes. The spike glycoprotein is a coronavirus surface protein involved in receptor binding and mediating

virus entry into host cells during infection (Li 2016). AZD1222 is a recombinant replication-defective chimpanzee adenovirus expressing the SARS-CoV-2 spike glycoprotein. Development of AZD1222 was initiated by the University of Oxford with subsequent transfer of development activities to the Sponsor.

On 30 December 2020, the UK Medicines and Healthcare products Regulatory Agency (MHRA) provided authorisation for emergency supply of AZD1222, and on 29 January 2021, the European Commission granted conditional marketing authorisation for the vaccine. Now known as COVID-19 Vaccine AstraZeneca, the vaccine in both jurisdictions is indicated for active immunisation to prevent COVID-19 caused by SARS-CoV-2, in individuals aged 18 years and older. The vaccination course consists of 2 separate intramuscular injections. The second dose should be administered between 4 and 12 weeks (28 to 84 days) after the first dose. Since May 2022, a booster dose may be given at least 3 months after the second dose. A booster dose of AZD1222 can also be given to adults who have had 2 doses of an authorised mRNA COVID-19 vaccine but is beyond the scope of this study. At the national level, public health bodies may issue official recommendations, taking into account emerging effectiveness data and the limited safety data.

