## 8. RESEARCH QUESTION AND OBJECTIVES

The primary study objectives are as follows:

- 1 To describe the baseline characteristics (eg, demographics, medical history) of all subjects in the *matched population*
- 2 To describe, among subjects who receive a first dose of AZD1222 (ie, in the *all AZD1222 vaccinated first dose population*), the timing and type of second dose of any COVID-19 vaccine (AZD1222 or other) over the study period
- 3 To describe the incidence rates (IRs) of prespecified AESIs in subjects who received at least 1 dose of AZD1222 in the *matched population* and subjects who did not receive any vaccination against COVID-19 (concurrent unvaccinated comparators) in the *matched population*
- 4 To estimate the relative and absolute risk of prespecified AESIs in subjects who received at least 1 dose of AZD1222 compared with concurrent unvaccinated comparators in the matched populations, using a retrospective cohort design and an SCRI design

Secondary objectives are as follows:

- 1 To describe the baseline characteristics (eg, demographics, medical history) of all subjects in the matched population among the specific populations considered to have missing information (Section 9.2.1.2)
- 2 To describe, among subjects who receive a first dose of AZD1222, (ie, in the *all AZD1222 vaccinated first dose population*), the timing and type of second dose of any COVID-19 vaccine (AZD1222 or other) over the study period among the specific populations considered to have missing information
- 3 To describe the IRs of prespecified AESIs in subjects who received at least 1 dose of AZD1222 in the *matched population* and subjects who did not receive any vaccination against COVID-19 (concurrent unvaccinated comparators) in the *matched population*, among the specific populations considered to have missing information
- 4 To estimate the relative and absolute risk of prespecified AESIs in subjects who received at least 1 dose of AZD1222 compared with concurrent unvaccinated comparators in the matched populations, among the specific populations considered to have missing information, using a retrospective cohort design and an SCRI design

Exploratory objectives are as follows:

- 1 To describe the IRs of prespecified AESIs in subjects who received an mRNA vaccine against COVID-19 (either Comirnaty or Spikevax) (active comparators) and in subjects

- from the pre-pandemic period (2017-2018) (historical comparators) in the matched population

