#### 9.2.1.1.2 ALL AZD1222 VACCINATED FIRST DOSE POPULATION

Among all subjects in the *all AZD1222 vaccinated population*, only those subjects that received AZD1222 as their first COVID-19 vaccine dose (subjects who received AZD1222 as their second or third, but not as first, COVID-19 vaccine dose will be excluded) will be included in the *all AZD1222 vaccinated first dose population*. To ensure a minimum quality of the data, subjects with missing values for age and sex will be excluded. This population will be included in the analysis to address primary objective 2 and secondary objective 2 (patterns of use). The **index date** will be the date when a subject received the first AZD1222 dose as their first COVID-19 vaccine dose ever.

An *all mRNA vaccinated first dose population* will also be generated in order to describe the patterns of use of the vaccines included in the active comparator cohort. This will include subjects who received at least 1 dose of an mRNA vaccine (Comirnaty or Spikevax) during the study period and for whom that dose was their first COVID-19 vaccine dose (subjects who received an mRNA vaccine as their second or third COVID-19 vaccine dose after a first dose with a vaccine other than mRNA will be excluded). Subjects with missing values for age and sex will be excluded. The **index date** will be the date when a subject received the first mRNA dose as their first COVID-19 vaccine dose ever.

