### 9.2.2 Study Period

The study period will start on the date AZD1222 vaccination began in each country. The first vaccinations started approximately 1 week after approval date, which was 30 December 2020 in the UK and 29 January 2021 in the EU. The study period duration will be 24 months in each data source or until latest data available at the time of start of data collection (data extraction), ie, this duration may include a few more months in the data sources where the lag time to obtain the data is shorter.

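### Second-dose use is reported as raw proportions, so people who leave before dose 2 are counted as first dose only and deaths are pooled with survivors who did not return (minor, descriptive)

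*Protocol*

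**What the plan says.** Primary objective 2 (Section 8) is to describe "the timing and type of second dose of any COVID-19 vaccine (AZD1222 or other) over the study period" among AZD1222 first-dose recipients. Secondary objective 2 repeats this in the special populations.

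Section 9.7.2 sets the measures:

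- The first row gives "Counts and proportions of subjects who received only the first dose of AZD1222".
- The second row, broken down by brand, gives "Counts and proportions of subjects who received a second dose of COVID-19 vaccine".
- The interval is summarised conditionally: "Among those who received 2 doses: the time (days) between the first and second doses will be described".

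The tables are produced overall, by sequential 3-month period and in the subgroups of special interest. They are also produced for people whose first dose was an mRNA vaccine.

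Section 9.2.1.1.2 defines the denominator. Beyond having AZD1222 as the first COVID-19 vaccine dose, the only condition is that "subjects with missing values for age and sex will be excluded". The mRNA population is defined in the same way, with entry at any time in the study period. Neither definition requires follow-up after dose 1.

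**The concern.** The first two rows together cover every first-dose recipient, so anyone without a recorded second dose falls into the first row whatever the reason. Three different situations are merged there:

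- **Alive and observed, no second dose.** This is the group that tells us about vaccine use.
- **Died before dose 2.** The label is literally true, but the death is mixed with non-return.
- **Deregistered, or data ended, before dose 2.** The label may be false. A person who moves away in week 5 may be vaccinated elsewhere, and their status is unknown.

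The tables are split where the chance of exit may differ. The frail group in Annex Table 2 includes people identified by palliative care or metastatic cancer. Section 9.9.1 says mRNA doses lie much closer together than AZD1222 doses, which leaves mRNA recipients less time to die or leave before dose 2. Differences between these tables could then partly reflect mortality, departure or length of observation.

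The interval summary does not repair this. It is conditional on having had two doses, so it does not show when, or how far, the whole cohort reached dose 2.

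**Working it through.** The protocol states no completion, mortality or deregistration rate, so there is no figure of its own to reproduce. Exit rate and completion below are assumptions, shown as ranges.

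**Inputs from the protocol.** Section 7: "The second dose should be administered between 4 and 12 weeks (28 to 84 days) after the first dose". Section 9.2.2: "The study period duration will be 24 months in each data source or until latest data available". Section 9.5 says AZD1222 was no longer administered by Interim Report 2, and Table 1 in Section 5 says that report covered the last period of administration. Table 4 gives VID counts of 484,145 first and 171 second doses (communication of 30 May 2021).

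**1. Exit before dose 2.** Let *h* be the annual rate of death or departure, *t* the day dose 2 falls, and *c* the share completing among those still observed at *t*.

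- Gone by day *t*: e = 1 − (1 − h)^(t/365.25)
- Reported first-dose-only share: 1 − c(1 − e)
- Share among those still observed: 1 − c
- Excess: c × e, which is never negative

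With c = 95%, so that 5.0% of those still observed do not complete:

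| Annual exit h | Gone by day 28 | Excess, day 28 (points) | Gone by day 84 | Excess, day 84 (points) |
|---|---|---|---|---|
| 0.5% | 0.04% | 0.04 | 0.12% | 0.11 |
| 1% | 0.08% | 0.07 | 0.23% | 0.22 |
| 2% | 0.15% | 0.15 | 0.46% | 0.44 |
| 5% | 0.39% | 0.37 | 1.17% | 1.11 |
| 10% | 0.80% | 0.76 | 2.39% | 2.27 |
| 20% | 1.70% | 1.61 | 5.00% | 4.75 |
| 30% | 2.70% | 2.56 | 7.88% | 7.48 |

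The result depends little on *c*. At h = 20% and day 84 the excess is 4.9 points with c = 98% and 4.0 with c = 80%. It depends strongly on the interval: at h = 20%, a second dose at day 84 rather than day 28 raises the first-dose-only share by 4.75 − 1.61 = 3.14 points with no difference in return. At h = 1% the same contrast is 0.22 − 0.07 = 0.15 points.

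**2. Running out of data.** Twenty-four months is 730.5 days, so a first dose has 84 days of follow-up if given by day 730.5 − 84 = 646.5, about month 21. If first doses end by month 18 (day 548), nobody is truncated. Only uniform uptake right up to month 24 gives 84/730.5 = 11.5%, and Section 9.5 rules that out for AZD1222.

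Early cuts differ. With uptake assumed uniform over 5 months (152.2 days) and a cut at month 6 (182.6 days), people vaccinated after day 98.6 have under 84 days: (152.2 − 98.6)/152.2 = 35%. At a month-9 cut the share is 0%. The VID counts show the extreme case: 1 − 171/484,145 = 99.96% first dose only, presumably mostly because dose 2 was not yet due or recorded.

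**3. What a competing-risk estimate changes.** Take h = 20%, day 84, c = 95%.

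- If every exit is a death, cumulative incidence of dose 2 with death competing is 0.95 × 0.95 = 90.25%. The complement is 9.75%, identical to the raw share (5.0 + 4.75).
- If every exit is a deregistration, treated as uninformative censoring, the estimate is 95% and the complement 5%.

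Cumulative incidence therefore corrects for leavers and truncated follow-up. Deaths must be separated by splitting the row.

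**The case against.** **The table is true as a description.** The objective asks for timing and type of second dose, and Section 9.7.2 never speaks of non-completion or refusal. A person who died in week 6 did receive only one dose. This stands for deaths, where the issue is pooling rather than error. It does not stand for leavers, whose second-dose status is unknown but is reported as known.

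**The detail belongs in the SAP.** Section 9.7 defers detailed methodology there, and the list in 9.7.2 is not exclusive. The SAP may well add categories or censoring rules, which limits the weight of the point. But the protocol does fix the measure and the denominator for a primary objective. It already treats enrolment termination and death as ends of cohort follow-up (9.2.3.1) and uses Kaplan-Meier estimates for adverse events with unknown risk windows (9.7.6).

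**Stronger readings are tempting.** A reader might infer that AZD1222 non-completion will be materially overstated in the final report because follow-up runs out. The documents point the other way, since administration had stopped well before the period closes. A reader might also infer that the distortion is known to be large and greatest in frail subjects. That is plausible, but no exit rate is given for any group, and a large ratio arises only by dividing by a small assumed non-return share. Finally, no formal comparison of uptake between AZD1222 and mRNA recipients is planned, so the interval effect matters only to someone who sets the two tables side by side.

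**The consequence is small.** No adverse-event rate or ratio uses this table. That stands in full.

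**Conclusion.** The point holds as a minor descriptive issue. As specified, the first-dose-only row mixes people observed without a second dose, people who died, and people whose status is unknown. Read as a measure of vaccine use, it can only be too high. In a population with 0.5 to 2% annual exit the excess is a fraction of a percentage point. It reaches several points only where exit is of the order of 10 to 30% a year and dose 2 comes late in the stated interval. These sizes rest on assumed exit rates, 95% completion and a single day for dose 2. Truncation by data end is confined to early data cuts and possibly late mRNA entrants. The adverse-event analyses are untouched.

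**What to change.** Make two additions to Section 9.7.2 (or to the SAP, if it does not already contain them):

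1. Split the first-dose-only row into three: alive and under observation without a second dose at a stated horizon (for example 18 weeks, already a boundary in the planned interval categories); died before dose 2; left or data ended before dose 2. This is the change that separates mortality from vaccine use.
2. Report the cumulative incidence of a second dose by brand from dose 1 (Aalen-Johansen), with death as a competing event and deregistration or data end as censoring, overall, by 3-month entry period and by special population. This corrects for leavers and late entrants. Its complement still contains the deaths, so it supplements item 1 and does not replace it.

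Both use vaccination, death and enrolment dates that the study already needs for follow-up. The cost is a few lines of specification and a small amount of extra programming in each data source.
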